Use of any experimental medication (including experimental vaccines other than the study vaccine) will lead to discontinuation of administration of any subsequent study vaccination. Participants may not receive an investigational drug (including investigational drugs for prophylaxis of COVID-19) or use an invasive investigational medical device within 30 days, or receive investigational or other immunoglobulin or monoclonal antibodies within 3 months, or receive convalescent serum for COVID-19 treatment within 4 months, or receive an investigational vaccine (including investigational Adenoviral-vectored vaccines) within 6 months before the planned administration of the first dose of study vaccine. During the study, the use of investigational vaccines other than the study vaccine is not allowed, and the use of investigational drugs is only allowed if medically indicated. Treatment with investigational COVID-19 drugs after diagnosis of a COVID-19 case is allowed during the follow-up period and needs to be recorded in the COVID-19 episode description.

Licensed live attenuated vaccines should be given at least 28 days before or at least 28 days after a study vaccination (14 days before and after for rotavirus vaccine in adolescents) and must be recorded. Other licensed (not live) vaccines (eg, the DTaP [reduced Diphtheria toxoid, Tetanus toxoid, and acellular Pertussis], influenza, tetanus, hepatitis A, hepatitis B, rabies) should be given at least 14 days before or at least 14 days after a study vaccination in order to avoid potential confusion of adverse reactions and potential immune interference and must be recorded.

The use of any coronavirus vaccine (licensed or investigational) other than Ad26.COV2.S is disallowed at any time prior to vaccination and during the study. If a vaccine is indicated in a post-exposure setting (eg, rabies or tetanus), it must take priority over the study vaccine and should

be discussed with the sponsor to determine if continued study vaccination is feasible, and any vaccinations must be recorded. Adolescents receiving routine immunizations according to their local vaccination schedules (eg, in Europe, the applicable national immunization schedules, and the equivalent in other countries) should not be postponed due to study participation and all vaccinations must be recorded.

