4. POPULATIONS (ANALYSIS SETS) FOR ANALYSIS

Analysis Sets	Description
Enrolled	All participants who sign the main ICF.
Randomized	The randomized analysis set includes all participants who were randomized in the study.
Full Analysis Set (FAS)	The Full Analysis Set will include all participants with at least one vaccine administration documented.

Analysis Sets	Description
Per Protocol Immunogenicity Set (PPI) ^a	The Per Protocol Immunogenicity population will include all randomized and vaccinated participants for whom immunogenicity data are available excluding data from participants with major protocol deviations expected to impact the immunogenicity outcomes (see details in Section 6.3). In addition, samples obtained after missed vaccinations, samples obtained from participants after SARS-CoV-2 infection (if confirmed by molecular testing or non-S-ELISA [or equivalent assay]), occurring during the study after randomization (if applicable), after other SARS-CoV-2 vaccination outside the study, and samples obtained outside pre-defined time windows will be excluded from the analysis set (see details in Sections 5.1.4 and 6.3).

^a If a participant is vaccinated out of window due to a study pause, this will not by default be a reason for excluding this participant from the PPI. Participants who were seronegative by local serology finger-prick test on Day 1 prior to study entry but were determined to be seropositive at baseline by central N- or S- serology testing will also be included (as the results from those assessments are not known prior to randomization).

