5. STATISTICAL ANALYSES

5.1. General Considerations

Details of the vaccine schedules associated to the primary vaccine regimen will be provided in the data presentation specification (DPS) document. Vaccination schedule have 2 components:

- Primary Vaccine Regimen (1-active dose or 2-active dose)
- Booster Vaccination (i.e. after unblinding)

Unless specified otherwise, analyses outputs will be produced by age group (12 to 15, 16 to 17, and overall). Where applicable, output will include results by dose level (1-active dose regimen and 2-active dose regimen combined) to report the post-dose 1 period.

All safety and immunogenicity data after a participant has received any other SARS-CoV-2 vaccine not part of the protocol will not be tabulated. Those data will be in listings.

A baseline (or reference) value will be defined as the value of the last available assessment prior to the first vaccination on Day 1, unless specified otherwise.

Unless otherwise stated, safety analyses will be conducted on the FAS, Immunogenicity analyses on the PPI.

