5.1.3. Phase Definitions

The phases in the Part 1 will be constructed as described in [Table 3](#).

Table 3: Phase Definitions

Phase	Phase #	Period	Period #	Interval	
				From	To
Screening	1			Date and time of signing the IC form	One second prior to start of post dose 1 period
Post-dose	2	Post-dose 1	1	Date and time of first vaccination	
Minimum of:
 
 a) 23:59:59 at the date of last contact (for early discontinuation) b) 23:59:59 at the date of data base cut-off date in case of interim analysis c) 23:59:59 on 28 days after the first vaccination (23:59:59 of day of vaccination + 28 days) d) One second prior to date and time of second vaccination e) One second prior to date and time of Booster Vaccination f) One second before date and time of another viral vaccination outside the study
Follow-up 1	3			One second after Post-dose 1 period end	
Minimum of:
 
 a) 23:59:59 at the date of last contact (for early discontinuation) b) 23:59:59 at the date of data base cut-off date in case of interim analysis c) One second prior to 6 months after first vaccination (vaccination date + 6 mths) d) One second prior to date and time of second vaccination e) One second prior to date and time of Booster Vaccination f) One second before date and time of another viral vaccination outside the study
Post-dose	2	Post-dose 2	2	Date and time of second vaccination	
Minimum of:
 
 a) 23:59:59 at the date of last contact (for early discontinuation) b) 23:59:59 at the date of data base cut-off date in case of interim analysis c) 23:59:59 on 28 days after the second vaccination (23:59:59 of day of vaccination + 28 days) d) One second prior to date and time of Booster Vaccination e) One second before date and time of another viral vaccination outside the study

Table 3: Phase Definitions

Phase	Phase #	Period	Period #	Interval	
				From	To
Follow-up 2	4			One second after Post-dose 2 period end	
Minimum of:
 
 a) 23:59:59 at the date of last contact (for early discontinuation) b) 23:59:59 at the date of data base cut-off date in case of interim analysis c) One second prior to 6 months after second vaccination (vaccination date + 6 mths) d) One second prior to date and time of Booster Vaccination e) One second before date and time of another viral vaccination outside the study

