Long term follow-up	5			One second after Follow-up 1 if only 1 dose was administered, and one second after Follow-up 2 if the 2 doses were administered	
Minimum of:
 
 a) Maximum of 23:59:59 at the date of last contact (for early discontinuation) and 23:59:59 at the date of last visit b) 23:59:59 at the date of data base cut-off date in case of interim analysis a) One second prior to date and time of Booster Vaccination b) One second before date and time of another viral vaccination outside the study c) One second prior to end of the study visit
Post-dose	2	Post-dose 3 (will be referred as Post-booster in the output)	3	Date and time of Booster Vaccination	
Minimum of:
 
 a) 23:59:59 at the date of last contact (for early discontinuation) b) 23:59:59 at the date of data base cut-off date in case of interim analysis c) 23:59:59 on 28 days after the Booster Vaccination d) One second before date and time of another viral vaccination outside the study
Booster follow-up 1	6			One second after Post-dose 3 period end	
Minimum of:
 
 a) 23:59:59 at the date of last contact (for early discontinuation) b) 23:59:59 at the date of data base cut-off date in case of interim analysis c) One second prior to 6 months after Booster Vaccination d) One second before date and time of another viral vaccination outside the study
Booster long term follow-up	7			One second after booster follow-up 1	
Minimum of:
 
 a) Maximum of 23:59:59 at the date of last contact (for early discontinuation) and 23:59:59 at the date of last visit b) 23:59:59 at the date of data base cut-off date in case of interim analysis c) One second before date and time of another viral vaccination outside the study d) One second prior to end of the study visit

Table 3: Phase Definitions

Phase	Phase #	Period	Period #	Interval	
				From	To
Follow-up other vaccine	8			Date and time of viral vaccination outside the study	Minimum of: a) Maximum of 23:59:59 at the date of last contact (for early discontinuation) and 23:59:59 at the date of last visit b) 23:59:59 at the date of data base cut-off date in case of interim analysis c) Date and time of end of the study visit

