5.1.3.1. Other Follow-up Visits

The following other time intervals will be derived for safety data summary as shown in [Table 4](#).

Table 4: Other Time Intervals

Time Intervals	From	To
Up to Day 85 (only for the primary analysis)	Date and time of first vaccination	Maximum of: a) Post-dose 1 end date b) Follow-up 1 end date c) Post-dose 2 end date
Primary Vaccination Period	Date and time of first vaccination	Maximum of: a) Post-dose 1 end date b) Follow-up 1 end date c) Post-dose 2 end date d) Follow-up 2 end date e) Long term follow-up
Booster Vaccination Period	Date and time of Booster Vaccination	Maximum of: a) Post-dose 3 end date b) Booster follow-up 1 end date c) Booster long term follow-up
Entire Study	Date and time of first vaccination	Maximum of: a) Primary Vaccination Period end date b) Booster Vaccination Period end date

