6.3. Appendix 3 The Per Protocol Immunogenicity population

The Per Protocol Immunogenicity population will include all randomized and vaccinated participants for whom immunogenicity data are available excluding participants with major protocol deviations expected to impact the immunogenicity outcomes and occurring on Day 1 or before.

In addition, samples obtained from participants will be excluded from the analysis set:

- a- after major protocol deviations expected to impact the immunogenicity outcomes and occurring after Day 1,
- b- after missed vaccinations,
- c- on or after natural SARS-CoV-2 infection (if confirmed by molecular testing or non-S-ELISA [or equivalent assay]) occurring during the study after randomization (if applicable),
- d- after other SARS-CoV-2 vaccination outside the study, or
- e- outside pre-defined time windows (Section 5.1.4).

In terms of derivation, the samples to consider for analysis on Per Protocol Immunogenicity must meet the following criteria:

Subject level

- **Crit1:** Must be randomized
- **Crit2:** Must be in FAS

- **Crit7:** No major protocol deviations with impact on immunogenicity on or before day 1 excluding Deviation Categories '85 for sample not in window', '87 for sample not stored properly'

Subject data level

Subject data to be excluded on and after the date of any of the following events:

- **Crit11:** seropositive post-Baseline by N-ELISA (value>LLOQ), if seronegative at baseline (as defined in Section [5.8.4](#))
- **Crit13:** SARS-CoV-2 infection occurring on or after Day 1
- **Crit20:** Major protocol deviations with impact on immunogenicity after day 1 except for deviation categories '85' or '87', which includes
 - **Crit21:** post SARS-CoV-2 viral vaccination outside the study occurring after Day 1
 - **Crit22:** Vacc 2 not in D57 +/- 8 days
 - **Crit23:** no Vacc 2, then exclude samples where the sample date>Day57+8.
 - **Crit24:** Vacc 3 not in D184 +180/-30 days post vacc1 – Groups 1, 2, 3
 - **Crit25:** no Vacc 3 (within 180 days post Day 184), then exclude samples where the sample date>Day184+30 – Groups 1, 2, 3

Vacc 2 refers to the 2nd dose of the primary regimen

Vacc 3 refers to booster

Sample level

Samples to be excluded on the date of deviation for '85' or '87' events:

- Crit30: major protocol deviations with impact on immunogenicity deviation categories '85' or '87', that is
 - **Crit31:** D1 sample not in window
 - **Crit32:** D29 sample not in window

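### SAP Table 3 ends every post-vaccination period at any outside viral vaccine, while the rest of the SAP means only another SARS-CoV-2 vaccine, so a permitted influenza vaccine takes later safety events out of the main summaries

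*SAP*

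**What the plan says.** SAP Table 3 defines each safety period by a start and by the earliest of several end dates. Post-dose 1, Follow-up 1, Post-dose 2, Follow-up 2, Long term follow-up, Post-dose 3, Booster follow-up 1 and Booster long term follow-up all include the end date "One second before date and time of another viral vaccination outside the study". Phase 8 (Follow-up other vaccine) starts at "Date and time of viral vaccination outside the study". None of these nine entries mentions SARS-CoV-2.

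Three other places in the SAP apply the same idea with a narrower trigger:

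- Section 5.1: "All safety and immunogenicity data after a participant has received any other SARS-CoV-2 vaccine not part of the protocol will not be tabulated"; such data go to listings.
- Section 4, PPI definition: samples are dropped "after other SARS-CoV-2 vaccination outside the study".
- Section 6.3, Crit21: "post SARS-CoV-2 viral vaccination outside the study occurring after Day 1".

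Protocol 6.7 expects other vaccines during the trial. Licensed non-live vaccines, with influenza, hepatitis A, hepatitis B and rabies among the examples, "should be given at least 14 days before or at least 14 days after a study vaccination". Routine immunizations "should not be postponed due to study participation and all vaccinations must be recorded".

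SAP 5.7.1.4 allocates unsolicited events to the period that contains their start. SAP Table 4 builds Entire Study from the later of the "Primary Vaccination Period end date" and its booster counterpart. Those two intervals are built from Phases 2 to 7 only.

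**The concern.** The primary safety endpoints in SAP 5.4.1 follow SAEs, AESIs and discontinuation-related MAAEs through to study end, and unsolicited AEs for 28 days after doses 1 and 2. The same 28-day window after the booster is a secondary endpoint. If the phase derivation is programmed from Table 3 as written, a routine influenza or hepatitis vaccine ends all of this follow-up for that participant in the post-dose, follow-up and Entire Study tables. Nothing in the SAP gives a reason for treating a non-COVID vaccine this way, and Section 5.1 limits exclusion from tables to a SARS-CoV-2 vaccine.

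The rule also fits poorly with continued dosing. Under protocol 7.1, a participant who receives another COVID-19 vaccine gets no more study vaccine, so a study dose should not normally follow the trigger. A participant who has an influenza vaccine carries on to dose 2 or the booster. The earliest-date rule then gives that later period an end before its start.

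**Working it through.** **Inputs**

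- Dose 2 on Day 57 and booster on Day 184 (Groups 1-3): SAP Table 1.
- Last visit on Day 240 (Groups 4-6) or Day 366 (Groups 1-3): protocol 1.3.2 and 1.3.1.
- A post-dose period is the vaccination day plus 28 days, or 29 calendar days: SAP Table 3.
- Spacing of 14 days for non-live vaccines: protocol 6.7. This allows Days 15 to 43 between doses (1 + 14; 57 - 14). It allows Day 71 onward after dose 2 (57 + 14), up to Day 170 before the booster (184 - 14), and again from Day 198 (184 + 14).
- Assumptions: on-schedule participants, six months taken as 183 days, and the outside vaccine placed at the start of its day.

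**Rule.** Let x be the day of the outside viral vaccine. Each end in Phases 2 to 7 is a minimum that includes the last second before x, so no period runs past Day x - 1. Entire Study ends at the maximum of those ends, so it keeps x - 1 days:

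- Share kept = (x - 1)/L, with L = 240 or 366.
- Post-dose 2 days = min(29, max(0, x - 57)).
- Post-booster days = min(29, max(0, x - 184)).

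**Results under the literal rule**

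| Outside vaccine | Entire Study kept, Groups 4-6 | Entire Study kept, Groups 1-3 | Post-dose 2 | Post-booster (Groups 1-3) |
|---|---|---|---|---|
| Day 15 | 14/240 = 5.8% | 14/366 = 3.8% | empty | empty |
| Day 43 | 42/240 = 17.5% | 42/366 = 11.5% | empty | empty |
| Day 71 | 70/240 = 29.2% | 70/366 = 19.1% | 14 of 29 days | empty |
| Day 170 | not shown | 169/366 = 46.2% | 29 of 29 | empty |
| Day 198 | not shown | 197/366 = 53.8% | 29 of 29 | 14 of 29 days |

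For Day 71, the computed end of Post-dose 3 falls 184 - 71 = 113 days before its start. Without an outside vaccine, the same rules carry Entire Study to the Day 240 visit or to the end of Day 366. Strictly, the Groups 4-6 interval stops just before Day 240. Using 239 days gives 70/239 = 29.3%, so the result does not change.

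**Softer reading.** Suppose the trigger acts only on the interval in which the vaccine falls. A vaccine given before a later study dose then no longer empties that dose's period or shortens Entire Study, though it still shortens the interval it falls in. A vaccine after the last dose has the same effect on Entire Study as before: 70 of 240 days for Day 71 in Groups 4-6, and 197 of 366 days for Day 198 in Groups 1-3. Post-dose 2 is still cut to 14 days by a Day 71 vaccine.

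**With the trigger limited to SARS-CoV-2 vaccines,** a non-COVID vaccine shortens nothing under either reading.

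**The case against.** The strongest reply is that the meaning is clear from context. Section 5.1 is the general rule for the section that contains Table 3, Phase 8 looks like the way to apply it, and Crit21 shows what may be the full phrase that Table 3 shortens. The programming instructions are in the Data Presentation Specifications, which are not available here, so nothing shows that the literal rule was coded. This is fair about intent. It does not rescue the text: Table 3 is the stated derivation rule, and it says something different from Section 5.1.

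Other limits also stand:

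- The empty periods depend on applying the earliest-date rule to a vaccine given before the period starts.
- Only viral vaccines fire the trigger. Tetanus and DTaP, in the same protocol list, do not.
- The percentages are shares of calendar time, not of events. Unsolicited AEs are generally collected for only 28 days after a dose, so within Post-dose 2 a Day 71 vaccine affects those starting on Days 71 to 85. The rest of the lost time matters mainly for MAAEs, SAEs and AESIs.
- Solicited AEs always stay in their post-dose period (SAP 5.7.1.4).
- Later events remain in Phase 8, and SAEs and AESIs also reach listings or narratives as appropriate (SAP 5.7.1.3). Safety is analyzed descriptively, with no test at stake.

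**Conclusion.** The concern holds. Table 3 contradicts SAP 5.1, the PPI definition and Crit21 in nine places. Followed as written, it takes safety events out of the summaries for a reason the SAP does not intend. For a participant with an influenza vaccine on Day 71, the literal rule leaves 29% (Groups 4-6) or 19% (Groups 1-3) of follow-up time in Entire Study. It also halves Post-dose 2 and, in Groups 1-3, empties the post-booster period. These are per-participant illustrations on the nominal schedule, and Day 71 is the earliest permitted day after dose 2. The total effect cannot be estimated, because the documents give no frequency of routine viral vaccination. A vaccine after the last study dose shortens Entire Study under both readings, so the point does not rest on the stricter one. It should be fixed, but it does not call the design into question.

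**What to change.** In the eight Table 3 end rules and the Phase 8 start, make the trigger a SARS-CoV-2 vaccination outside the study, matching SAP 5.1, the PPI definition and Crit21. Events after such a vaccine stay in listings, as Section 5.1 already provides. Table 4 needs no change.

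The cost is one qualifier in nine places and the matching condition in the phase-derivation program, with no new data or outputs. SAP Section 2 shows that the primary analysis has already been run, so the program should be checked for which trigger it used. If it used the literal one, the issued tables need checking for participants with a recorded non-COVID viral vaccine.

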5.1.3.1. Other Follow-up Visits

The following other time intervals will be derived for safety data summary as shown in [Table 4](#).

Table 4: Other Time Intervals

Time Intervals	From	To
Up to Day 85 (only for the primary analysis)	Date and time of first vaccination	Maximum of: a) Post-dose 1 end date b) Follow-up 1 end date c) Post-dose 2 end date
Primary Vaccination Period	Date and time of first vaccination	Maximum of: a) Post-dose 1 end date b) Follow-up 1 end date c) Post-dose 2 end date d) Follow-up 2 end date e) Long term follow-up
Booster Vaccination Period	Date and time of Booster Vaccination	Maximum of: a) Post-dose 3 end date b) Booster follow-up 1 end date c) Booster long term follow-up
Entire Study	Date and time of first vaccination	Maximum of: a) Primary Vaccination Period end date b) Booster Vaccination Period end date

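### For participants who miss dose 2 but stay in follow-up, the SAP's Day 85 safety interval has no Day 85 cap and can run to about Day 182–185

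*SAP*

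**What the plan says.** SAP Section 5.1.3.1 (Table 4) lists additional time intervals for the safety summaries. One is labelled "Up to Day 85 (only for the primary analysis". It starts at the first vaccination and ends at the maximum of three dates: the end of Post-dose 1, the end of Follow-up 1 ("b) Follow-up 1 end date") and the end of Post-dose 2.

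Those end dates come from SAP Section 5.1.3 (Table 3), where each is a minimum of several limits. For Follow-up 1 the limits are:

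- last contact, for a participant who discontinues early
- the data cut-off, which the table words as "b) 23:59:59 at the date of data base cut-off date in case of interim analysis"
- the six-month limit, which it words as "c) One second prior to 6 months after first vaccination (vaccination date + 6 mths"
- the start of dose 2, which it words as "d) One second prior to date and time of second vaccination"
- the booster, less one second
- any viral vaccine received elsewhere, less one second

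Post-dose 2 exists only if a second vaccination, active or placebo, was given. Its longest limit is "c) 23:59:59 on 28 days after the second vaccination (23:59:59 of day of vaccination + 28 days".

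SAP Section 5.9 limits the primary analysis to data through 28 days after dose 2. Protocol Section 7.1 keeps participants whose further vaccination is withheld in the study for safety and immunogenicity follow-up. Protocol Section 8 (Visit Windows) schedules the visits after a missed vaccination from its planned date.

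**The concern.** The label promises a fixed horizon, but neither table contains a Day 85 limit. The interval stops near Day 85 only because dose 2 cuts Follow-up 1 short and starts a 28-day Post-dose 2 period. For a participant who misses dose 2 and stays in the study, neither happens, and the maximum falls on Follow-up 1, which can last six months from dose 1.

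A primary-analysis table labelled to Day 85 could then count later events for these participants and for no one else. They are not a random subset. The reasons for withholding vaccination in Protocol Section 7.1 include related AEs, related SAEs or Grade 4 events, anaphylaxis, and TTS, GBS or MIS-C. Some participants would therefore be observed for longer because of an earlier safety event. With about 50 participants per group, one or two late events can change a displayed rate.

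**Working it through.** **Inputs.** Dose 2 is planned for Day 57 with a window of −3/+7 days, so Days 54 to 64 (Protocol Sections 1.3.1 and 1.3.2). Study Day is the date minus the dose 1 date plus 1 (SAP Section 5.1.1). Period ends follow SAP Table 3 and the interval end follows SAP Table 4. The enrolment target is about 300.

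**1. Reproduce the label.** With dose 2 on Day 57, Follow-up 1 ends just before dose 2 and Post-dose 2 ends on Day 57 + 28 = Day 85. The maximum is Day 85, as labelled. Across the visit window, 54 + 28 = Day 82 and 64 + 28 = Day 92.

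**2. Remove dose 2, participant still followed.** Post-dose 1 ends on Day 1 + 28 = Day 29. Follow-up 1 ends one second before six calendar months after dose 1. Six months span 181 to 184 days depending on the start date, which gives Study Day 182 to 185. There is no Post-dose 2 period, so the maximum of the remaining two dates is Day 182–185.

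**3. Apply the other limits, still without dose 2.**

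| Situation | Interval ends |
|---|---|
| Last contact Day 40 | Day 40 |
| Last contact Day 100 | Day 100 |
| Outside vaccination Day 60 | Day 60 (one second before the vaccination) |
| Cut-off at Day 85, 120 or 150, if the cut-off limit applies | Day 85, 120 or 150 |
| Cut-off at Day 184 or later | 6-month limit (Day 183 for a dose 1 date of 15 October 2021) |

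The six-month figure is therefore an upper end, and some participants without dose 2 stop before Day 85.

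**4. Which events can be affected.** Solicited AEs are always allocated to their post-dose period (SAP Section 5.7.1.4) and are collected for 7 days. Most other unsolicited AEs are collected for 28 days after each vaccination (Protocol Section 8.3.1). SAEs, AESIs and AEs leading to discontinuation are collected throughout the study, and MAAEs to 6 months after each vaccination. These categories can contribute events after Day 85.

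**5. Size.** For one participant followed to Day 184, the interval is 184/85 = 2.16 times the labelled length, an excess of 184 − 85 = 99 days. The documents give no count of such participants, so the shares below are assumptions. Nominal person-time is 300 × 85 = 25,500 days.

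| Assumed share without dose 2, followed to Day 184 | Participants | Excess days | Excess, % of nominal |
|---|---|---|---|
| 1% | 3 | 3 × 99 = 297 | 1.2% |
| 5% | 15 | 15 × 99 = 1,485 | 5.8% |
| 10% | 30 | 30 × 99 = 2,970 | 11.6% |

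**The case against.** The strongest reply is that the intended scope is clear elsewhere. SAP Section 5.9 limits the primary analysis to 28 days after dose 2, and the protocol's visit rule gives a participant who missed dose 2 a nominal Day 85. This shows what was meant, but a programmer following Table 4 would not obtain it: the stated derivation contains no such limit.

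A second reply is that the data cut-off would end the interval. That limit is worded for an interim analysis, and SAP Section 5.9 lists interim and primary analyses separately, so it is unclear whether it applies. If it does, it is a single calendar date. Enrolment began on 29 September 2021 and was slow (protocol amendment summary), so a cut-off late enough for the last participant's Day 85 would fall well beyond Day 85 for early enrollees.

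Other parts of the reply stand:

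- Safety results are also presented by phase and period, which keeps Post-dose 1 and Follow-up 1 events apart.
- The MAAE endpoint itself runs to 6 months after the last dose, so such events are legitimate data under the wrong label.
- Participants with dose 2 do not all end exactly on Day 85 either.
- Protocol Section 7.1 also lists reasons unrelated to safety, such as pregnancy, unblinding and withdrawal of consent to further vaccination, and gives no shares.

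A reader might infer that everyone without a second dose is followed to six months under this label. The limits in step 3 rule that out. A reader might also infer that dose selection was distorted. The primary analysis does inform the selected dose level, but no formal safety testing is planned, and the guidelines in SAP Section 5.9.1 concern Grade 3 reactogenicity and are not to be assessed in this study. The documents do not show that any post-Day-85 event affected a decision.

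**Conclusion.** The end rule is wrong as written for one group: participants who miss dose 2 and remain in follow-up. Their interval can reach Day 182–185, against both its label and the stated scope of the primary analysis. The effect is confined to SAEs, AESIs, MAAEs and AEs leading to discontinuation.

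The expected size is minor. The factor of 2.16 is roughly a per-person ceiling, and the person-time figures rest on assumed shares and on every such participant reaching Day 184. Whether any produced table is affected depends on the number of these participants, whether the cut-off limit was applied, and whether the SAP version in force at the primary analysis carried the same line. The documents settle none of these.

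**What to change.** Replace the end rule for this interval in SAP Table 4:

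- If dose 2 was given, end at the Post-dose 2 end date.
- Otherwise, end at the earlier of (i) the later of the Post-dose 1 and Follow-up 1 end dates and (ii) 23:59:59 of Day 85.

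The Post-dose 1 date must stay in the second branch. If last contact falls within 28 days of dose 1, Follow-up 1 would be empty and could not supply a valid end date.

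The text change is one table entry. It needs no new data and leaves participants who received dose 2 unchanged. It is not sufficient alone, because SAP version 5.0 already refers to primary-analysis results (Sections 2 and 5.8.4) and this interval serves only that analysis. The sponsor should also count participants without dose 2 whose interval passed Day 85, check for later SAEs, AESIs, MAAEs or AEs leading to discontinuation, and re-run or footnote any primary-analysis table that includes them. If there are none, a sentence in the study report closes the point.
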